7.5.3.7 Anti-KRN23 Antibody Screening

To determine the immunogenicity profile of KRN23, blood samples will be obtained for analysis of ADA pre-dose at Weeks 0, 4, 12, 24, 36, 48, 72, 96, 120, 144, and every 24 weeks as applicable through the EoT Visit as indicated in [Table 2.1](#) and [Table 2.2](#). The concentration of anti-KRN23 antibodies in human serum will be determined using a validated sandwich enzyme-linked immunosorbent assay (ELISA) and a 2-tiered strategy: screening assay and specificity confirmation assay. If the development of anti-KRN23 antibodies is suspected in a given subject, samples may be obtained at additional time points on a case-by-case basis, if warranted.

7.5.3.8 Renal Ultrasound

Renal ultrasounds will be conducted at Screening and at Weeks 24, 48, 72, 96, 120, 144, and every 24 weeks as applicable through the EoT Visit as indicated in [Table 2.1](#) and [Table 2.2](#). The ultrasound may be performed either before or after administration of KRN23 while on treatment. The screening ultrasound will be interpreted by qualified personnel at the investigational site to determine eligibility and to serve as Baseline data. However, central readings will be performed for all on-treatment renal ultrasounds to evaluate changes in calcifications and all other renal abnormalities from Baseline. Ratings will be performed by a single central reader.

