7.5.1.2.1 Bone Health Measurements

Standard radiographs will be obtained predose- at Week 0 and at Weeks 12, 24, 36, 48, 72, 96, 120, 144, and every 24 weeks as applicable through the EoT Visit until identified fractures/pseudofractures resolve. Standard radiographs will be obtained of the chest, lateral spine, right and left hand/wrist, right and left humerus, right and left radius/ulna, right and left femur/pelvis, right and left tibia/fibula, and right and left foot as well as any location(s) where the subject is currently experiencing tenderness or pain that may reflect underlying pathology, or where the subject has a history of recent (<3 months) fracture, or in bones where radiographs suggest the presence of a fracture or pseudo-fracture. Radiographs will be interpreted locally for the identification of new abnormalities, and on treatment- radiographs will be compared to Screening radiographs by 3 trained central readers (2 primary and 1 adjudicator) who are blinded to post-treatment time point and subject data. At each

on-treatment time point, the radiograph will be compared to Baseline and rated by the 3 central readers, using a pre-defined list of abnormalities. Central readers will be blinded to other patient data.

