7.6.2.8.5 Renal Ultrasound

Renal ultrasound data will be listed and summarized for each subject and study population. Individual subject ultrasound results will be examined in relation to the subjects' Screening ultrasound, and the overall renal ultrasound results will be summarized.

The SAP will provide additional details on the planned safety analyses.

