## **8.2 Demographics and Baseline Characteristics**

Summaries of demographic characteristics will include descriptive statistics for age, height, weight, BMI, renal ultrasound scores, baseline skeletal survey radiographs measures (mean, standard deviation, median, minimum and maximum values) and for sex, race, ethnicity, PHEX mutation, radiograph location (number and percentage of subjects in each category).

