## 8.6 General Safety

All safety analyses will be performed on the safety analysis set, unless stated otherwise. General safety will include AEs, treatment related AEs, SAEs, AE of injection site reaction (grouped by High-Level Group Term), laboratory measurements including chemistry, hematology, and urinalysis parameters, GFR, amylase, HAHA, concomitant medications, physical exams, pregnancy test and vital signs. No hypothesis testing is planned for safety data.

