#### **8.7.1 Renal Ultrasound**

Renal ultrasound will be conducted with findings of nephrocalcinosis graded on a 5-point scale and by a central reader. These results will be summarized by time point. Furthermore, a grade shift table summarizing changes from baseline by time point will also be created.

The number and percentage of subjects with nephrolithiasis observed in the kidney will be summarized by time point. A shift table summarizing changes from baseline by time point will be created.

A listing of renal ultrasound nephrocalcinosis scores, the presence or absence of nephrolithiasis in the kidney and the radiologist's comments will also be provided.

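### Renal ultrasound Baseline is a site reading while on-treatment scans are read centrally, and the SAP does not say who grades Baseline, so the shift tables may mix readers

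*Protocol*

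**What the plan says.** Protocol 7.5.3.8 gives the two readings to different people. For Screening: "The screening ultrasound will be interpreted by qualified personnel at the investigational site to determine eligibility and to serve as Baseline data". For later scans: "central readings will be performed for all on-treatment renal ultrasounds to evaluate changes in calcifications" and in other renal abnormalities relative to Baseline, with ratings by one central reader. The on-treatment scans are scheduled for Weeks 24, 48, 72, 96, 120 and 144, and every 24 weeks after that as applicable.

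Protocol 7.6.2.8.5 sets the comparison without naming a reader: "Individual subject ultrasound results will be examined in relation to the subjects' Screening ultrasound".

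SAP 8.7.1 supplies the scale and the tables: "Renal ultrasound will be conducted with findings of nephrocalcinosis graded on a 5-point scale and by a central reader". It adds that "a grade shift table summarizing changes from baseline by time point will also be created", and plans a second shift table for nephrolithiasis. SAP 8.2 includes the scores among the baseline characteristics ("descriptive statistics for age, height, weight, BMI, renal ultrasound scores"), again with no reader named. SAP 5.1 takes the last non-missing value before the first dose as Baseline, which does not choose between two readings of the same scan.

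Neither document says that sites assign the 5-point grade, or that the central reader re-reads the Screening scan.

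**The concern.** Change from baseline in renal ultrasound is listed among the primary safety endpoints (Protocol 7.6.1.1) and the ectopic mineralization endpoints (Protocol 7.6.2.8). If Baseline is graded by site staff and every later scan by one central reader, any systematic difference between them enters every shift from baseline. A central reader who grades higher than the sites would produce apparent progression; one who grades lower would conceal real progression. There is no concurrent control group in which the same offset would appear and could be subtracted.

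The point is sharpest at the Week 24 analysis, which SAP 3.6 says may support regulatory filings. Week 24 is the first on-treatment ultrasound, so each subject then has one central reading and no on-treatment trend against which to judge a step.

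The protocol handles radiographs differently. In Protocol 7.5.1.2.1, on-treatment "radiographs will be compared to Screening radiographs by 3 trained central readers". No matching rule is written for renal ultrasound.

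**Working it through.** The plan states no figure on this point, so there is none to reproduce. The check sets the texts side by side and then illustrates the possible size.

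**Step 1: who reads what**

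| Source | Screening/Baseline scan | On-treatment scans |
|---|---|---|
| Protocol 7.5.3.8 | Site personnel; this reading is Baseline | Single central reader |
| Protocol 7.6.2.8.5 | Is the reference scan; reader not named | Reader not named |
| SAP 8.7.1 | Not addressed separately | Central reader, 5-point scale |
| SAP 8.2 | Scores summarised; reader not named | Not applicable |
| SAP 5.1 | Last pre-dose value; does not choose between readings | Not applicable |

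Two readings are possible. If the protocol governs Baseline, the shift tables are local-to-central, and the site would have to supply a grade on a scale that no text tells it to use. If SAP 8.7.1 silently covers Screening, the tables use one reader but depart from the protocol's express Baseline. The documents need reconciling in either case.

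**Step 2: possible size under the first reading**

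Inputs: n = 20 subjects (Protocol synopsis, number planned). q is the assumed probability that a subject with no true change is graded higher centrally than locally. The documents give no value for q, so 2%, 10% and 30% are shown. Subjects are treated as independent.

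- Expected false worsenings = 20q
- P(at least 1) = 1 − (1 − q)^20
- P(at least 2) = 1 − (1 − q)^20 − 20q(1 − q)^19

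| q | Expected | P(≥ 1) | P(≥ 2) |
|---|---|---|---|
| 0.02 | 0.4 | 0.332 | 0.060 |
| 0.10 | 2 | 0.878 | 0.608 |
| 0.30 | 6 | 0.999 | 0.992 |

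Effect on the reported proportion (exact Clopper-Pearson 95% intervals): a true 0/20 has interval 0 to 16.8%. At q = 0.10 it would be reported as about 2/20, or 10% (1.2 to 31.7%). At q = 0.30 it would be about 6/20, or 30% (11.9 to 54.3%).

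**Step 3: sensitivity to independence**

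Local readers belong to sites, and the synopsis allows up to 5. At the extreme, take 5 equal sites of 20/5 = 4 subjects, where with probability 0.10 a whole site reads low. Then P(at least 1) = 1 − 0.9^5 = 0.41 instead of 0.88. The expected count is still 5 × 4 × 0.10 = 2, but any occurrence would affect at least 4 of the 20 subjects. Clustering makes a false signal less likely but larger when it occurs.

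**The case against.** The strongest reply is that the SAP already intends central grading throughout. The shift tables exist only in SAP 8.7.1; the protocol leaves safety analysis detail to the SAP. That section names a central reader and excludes no time point. A grade shift also needs both grades on one scale, and the central reader is the only grader named. A central reader asked to evaluate change from Baseline plausibly has the Screening images in hand. On this view there is a wording gap and no mixing.

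The reading is possible, and it is why the conclusion is that the tables *may* mix readers. It does not remove the problem. The protocol states in terms that the site reading is Baseline and contrasts it with central reading of on-treatment scans; no text provides for a central re-read. A SAP that used a central Baseline would contradict the protocol.

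Several points on impact stand:

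- On-treatment visits share one reader, so progression after Week 24 can still be assessed.
- A constant offset would show as a step at Week 24 that does not grow.
- The analysis is descriptive; SAP 8.6 says "No hypothesis testing is planned for safety data", and renal ultrasound is not among the safety variables that SAP 8.1.1 selects for p-values.
- Mineralization is also followed by centrally read echocardiography and by serum and urine chemistry.
- The disagreement rates above are assumed, as is their direction.

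Imaging detail might also sit in a study manual, which cannot be checked from these documents.

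**Conclusion.** The concern holds. As written, the protocol puts a local-versus-central difference into every renal ultrasound shift from baseline, and the SAP neither adopts nor overrides that Baseline. This should be fixed. Sample size, alpha and power are unaffected. What is at risk is the meaning of two descriptive tables for a listed safety endpoint, most of all at Week 24, when no later central scan is available to expose an offset.

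The size is unknown. Over the assumed range of 2% to 30%, between 0.4 and 6 of 20 subjects would be expected to show worsening that comes only from the change of reader. That range rests on assumed rates, on all disagreement running upward, and on following the protocol's Baseline literally; the chance of at least one such case also rests on independence between subjects. If the Screening scans were in fact graded centrally, the tables are sound and only the contradiction between the documents remains. Confidence is medium for that reason.

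**What to change.** Keep the site reading for eligibility. Have the existing central reader grade the Screening images on the same 5-point scale and record nephrolithiasis. Define that central reading as Baseline for analysis in Protocol 7.5.3.8 and 7.6.2.8.5 and in SAP 8.2 and 8.7.1. Masking the reader to visit would help where feasible, but it goes beyond what closes the gap.

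If a Screening image cannot be retrieved, flag that subject's shift as local-to-central and also show shifts from the first on-treatment central reading (Week 24).

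The cost is about 20 extra reads plus wording in both documents, with no new scan and no new reader. Two limits apply. The documents do not say that Screening images were retained or can be transferred. The Week 24 fallback is already on treatment, so it misses any change before then.

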7.5.3.9 Echocardiogram

ECHO will be performed pre-dose at Week 0 and either before or after administration of KRN23 at Weeks 24, 48, 72, 96, 120, 144, and every 24 weeks as applicable through the EoT Visit. The goal is twofold: 1) assess for evidence of ectopic mineralization in the heart and aorta, and 2) evaluate for signs of LVH or cardiac dysfunction. Additional tests may be performed if any abnormalities are detected or if medically indicated. ECHO administration procedures will be standardized and results will be read centrally by trained personnel who are blinded to the dose and dose regimen of the subjects. ECHOs will be assessed for any clinically significant abnormality or relevant changes from Baseline (CFB), and new evidence of cardiac calcifications, LVH, or other new abnormalities will be recorded as TEAEs.

7.5.3.10 Electrocardiogram

A standardized 12-lead ECG will measure PR, QRS, QT, and corrected QT (QTc) intervals pre-dose at Week 0 and either before or after administration of KRN23 at Weeks 24, 48, 72, 96, 120, 144, and every 24 weeks as applicable through the EoT Visit. The goal is to evaluate for changes associated with LVH, as well as for changes in conductivity and intervals. ECG administration procedures will be standardized and results will be read locally by trained site personnel. A medically qualified person will assess the ECG results for any clinically significant abnormality that would exclude a subject from eligibility in the study and for clinically relevant changes between examinations. Copies of the ECGs should be kept with the subject's source documents. New evidence of LVH or other new abnormalities will be recorded as TEAEs.

7.5.3.11 Pregnancy Testing

Female subjects of child-bearing potential must be non-pregnant and non-nursing and will have urine pregnancy tests pre-dose at all dosing visits and at EoT, as indicated in [Table 2.1](#) and [Table 2.2](#). A serum pregnancy test will be performed in the event of a positive or equivocal urine pregnancy test result. In the event of a positive urine pregnancy test at an HH visit, KRN23 will not be administered and a serum sample will be drawn for confirmation of pregnancy. Female subjects with a positive serum pregnancy test at Screening will not be enrolled in the study. Female subjects with a positive serum pregnancy test at Baseline or any subsequent visit will be discontinued from the study.

Experience with KRN23 in pregnant women is limited. The study drug may involve risks to a pregnant female or unborn baby that are currently unknown. Female participants of child-bearing potential who have not undergone a total hysterectomy or bilateral salpingo-oophorectomy and are sexually active must consent to use a highly effective method of contraception as listed below from the period following the signing of the informed consent through 12 weeks (approximately 5 times the elimination half-life) after stopping the study drug. Sexually active male participants with female partners of childbearing potential must consent to use a condom with spermicide or a highly effective method of contraception

listed below from the period following the signing of informed consent through 12 weeks after stopping the study drug. Examples of highly effective methods include:

- Combined (estrogen and progestogen containing) hormonal contraception associated with inhibition of ovulation (e.g. oral, intravaginal, transdermal)
- Progestogen-only hormonal contraception associated with inhibition of ovulation (e.g. oral, injectable, implantable)
- Intrauterine device (IUD) or intrauterine hormone-releasing system (IUS)
- Bilateral tubal occlusion
- Male sterilization, also called vasectomy
- Sexual abstinence (i.e., refraining from heterosexual intercourse during the entire period of risk associated with the study treatments, when this is in line with the preferred and usual lifestyle of the subject)

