Rationale: Currently, some subjects are self-administering or having their caregiver administer KRN23 in the home setting with HH nurse supervision. The requirement for HH nurse supervision of KRN23 administration by subject is being removed to provide increased flexibility for the subjects. Instructions for Use have been developed with input from healthy volunteers and patients with XLH. These instructions will be used to guide subjects and caregivers through the injection process. The Instructions for Use will be approved by sites and IRBs before subject/caregiver administration begins.

- 2. Schedule of Events:** The Schedule of Events has been updated to have a HH nurse required only on HH visits occurring every 12 weeks after week 96 to ensure

collection of vital signs, pregnancy testing, and documentation of concomitant medications and AEs. A HH nurse is no longer required at all other HH visits as long as the subject or caregiver has been properly trained and instructed to handle and administer study drug. Assessments collected by the HH nurse at HH visits occurring every 4 weeks will now be collected every 12 weeks at a HH visit or a clinic visit. Language was added to clarify that subjects will not be required to complete two patient-reported outcomes – the Brief Pain Inventory (BPI) and Short Form Health Survey (SF-36) – past Week 144. Additionally, language describing the visit window in the Schedule of Events was corrected to reflect all visits prior to the End of Treatment (EoT) visit.

Rationale: Since supervision is no longer required in the event that drug is administered by the subject or caregiver, assessments previously made by the HH nurse, including pregnancy testing and vital signs, will no longer be collected during every HH visit. However, a HH nurse must be present at HH visits occurring every 12 weeks to ensure accurate safety assessments. The patient-reported outcomes, BPI and SF-36, are not required past Week 144. Extending the visits from 25 to 43 was intended to be made in the Protocol Amendment 1. The additional visits and visit windows were noted in the Protocol Amendment 1, Section 7.5 Study Procedures and Assessments, page 40, but not included in the Schedule of Events footnote section.

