Subjects will receive the initial SC injection of KRN23 at the clinic. Starting doses will be individual for each subject, i.e., the subject's last dose in study KRN23-INT-001 or KRN23-INT-002, either 0.3, 0.6, or 1.0 mg/kg. Up to Week 12, individual subjects who have not reached serum phosphorus levels above the lower limit of normal (LLN; 2.5 mg/dL) at the end of the dose interval may have their doses titrated upward every 4 weeks to a maximum dose of 1.0 mg/kg based on fasting trough serum phosphorus levels. Doses may be titrated downward if at any point the serum phosphorus level increases above the upper limit of normal (ULN; 4.5 mg/dL). KRN23 will be administered monthly (every 4 weeks), either at home or in the clinic. Subjects will return to the clinic monthly at Weeks 4, 8, and 12; then every 12 weeks at Weeks 24, 36, and 48; and then every 24 weeks at weeks 72, 96, 120, 144 and as applicable up until the End-of-Treatment (EoT) Visit, which will occur by 30 September 2018. Subjects may be seen at home by Home Health (HH) personnel between the clinic visits, or the HH visits may be completed in the clinic, depending on the proximity of the subjects to the investigational site and the location and availability of HH resources. After proper training, subjects may self-administer KRN23 or be administered KRN23 by caregivers without the supervision of HH nurse; in such cases, the HH visit would become a telephone visit.

Safety, immunogenicity, PK, PD, and efficacy assessments will be performed during the treatment period as outlined in the Schedule of Events. All assessments, with the exception of weight, will be repeated at the EoT Visit. Subjects may choose to withdraw from the study at any time.

NUMBER OF SUBJECTS PLANNED:

Twenty subjects will be enrolled in this study.

DIAGNOSIS AND CRITERIA FOR INCLUSION AND EXCLUSION:

INCLUSION CRITERIA:

Subjects eligible for enrollment in the study must meet all of the following criteria at Screening:

1. Have participated in KHK's KRN23-INT-001 or KRN23-INT-002 studies (received at least 2 doses of KRN23)
2. Estimated glomerular filtration rate (eGFR) ≥ 60 mL/min (using the Chronic Kidney Disease Epidemiology Collaboration [CKD-EPI] equation) or eGFR of 45 to <60 mL/min at Screening

with confirmation that the renal insufficiency is not due to nephrocalcinosis

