Urine Pregnancy Test ⁸		X	X	X	
Vital Signs ⁹		X	X	X	
Height			X	X	
Physical Examination			X	X	
PHEX mutation analysis ¹⁰					
Anti-KRN23 antibody (ADA) ^{11,12}			X	X	

VISIT TYPE / NUMBER	HH ³ or TC ¹⁹ 27, 28, 29, 30, 31, 33, 34, 36, 37, 39, 40, 42, 43, 45, 46, and as applicable thereafter until 30 September 2018	HH ²⁰ 35, 41, and as applicable thereafter until 30 September 2018	32, 38, 44, and as applicable thereafter until 30 September 2018	EoT ²¹ visit number will vary for each subject	Safety Follow-up TC ²²
WEEK ⁴	Every 4 Weeks: 76, 80, 84, 88, 92, 100, 104, 112, 116, 124, 128, 136, 140, 148, 152, and as applicable thereafter until 30 September 2018	Every 12 Weeks: 108, 132 and as applicable thereafter until 30 September 2018	Every 24 Weeks: 96, 120, 144, and as applicable thereafter until 30 September 2018	Last visit occurring by 30 September 2018 ²¹	4 weeks (and, if applicable, 8 weeks) after EoT Visit ²²
Serum Phosphorus			X	X	
Serum Calcium			X	X	
Serum Creatinine			X	X	
Serum iPTH			X	X	
Serum FGF23 ¹²			X	X	
Serum 1,25(OH) ₂ D			X	X	
Bone Biomarkers ¹⁴			X	X	
ECHO, ECG			X	X	
BPI, SF-36 ¹⁵			X ¹⁵	X ¹⁵	
WOMAC ¹⁶					
6MWT, TUG					
X-Ray ¹⁷			X	X	
Interval History			X	X	
Serum KRN23 ^{12,18}			X	X	
Prior and Concomitant Medications	X	X	X	X	X

VISIT TYPE / NUMBER	HH ³ or TC ¹⁹ 27, 28, 29, 30, 31, 33, 34, 36, 37, 39, 40, 42, 43, 45, 46, and as applicable thereafter until 30 September 2018	HH ²⁰ 35, 41, and as applicable thereafter until 30 September 2018	32, 38, 44, and as applicable thereafter until 30 September 2018	EoT ²¹ visit number will vary for each subject	Safety Follow-up TC ²²
WEEK ⁴	Every 4 Weeks: 76, 80, 84, 88, 92, 100, 104, 112, 116, 124, 128, 136, 140, 148, 152, and as applicable thereafter until 30 September 2018	Every 12 Weeks: 108, 132 and as applicable thereafter until 30 September 2018	Every 24 Weeks: 96, 120, 144, and as applicable thereafter until 30 September 2018	Last visit occurring by 30 September 2018 ²¹	4 weeks (and, if applicable, 8 weeks) after EoT Visit ²²
Adverse Events	X	X	X	X	X
Weight			X	X	
Drug Administration ¹⁹	X	X	X		

Footnotes for Table 2.1 and Table 2.2

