19 After proper training, subjects or their caregiver will administer study drug under the supervision of a healthcare provider. If the subject or caregiver demonstrates competency in administration of SC injections at that time, they will be instructed to perform future study drug administrations at home without supervision for HH visits occurring after week 96 or later (with the exception of site visits, during which subject/caregiver administration is preferable to demonstrate continued competency in technique, but not required). Drug administration by a HH nurse may continue at the discretion of the investigator, subject and/or caregiver. If the healthcare provider determines that the subject/caregiver requires additional training on SC injection technique, study drug will again be administered under the supervision of a healthcare provider at the next study visit. Once a subject or their caregiver has received appropriate SC injection technique training and begins administering study drug at home without supervision, they will be contacted via telephone by the study site every 28 days (+ 5 days), with the exception of site visits, to confirm administration of study drug and to record concomitant medications and AEs. Telephone visits may also be conducted at the clinical site depending on proximity of the subject to the site.

20 For subjects that are self-administering or having a caregiver administer study drug, a healthcare provider will return for HH visits occurring every 12 weeks after week 96 or visit 32 to assess vital signs, pregnancy, and record concomitant medications and AEs.

21 If a subject will be continuing KRN23 treatment under commercial use or another mechanism, the first dose of that treatment should not be administered until after completion of all of the EoT Visit assessments. Those subjects who terminate the study early will be asked to come back to the clinic for a final assessment. If the subject terminates the study early before Week 72, then the Week 72 assessments will be conducted. If the subject terminates the study early between Weeks 72 and EoT Visit (up until 30 September 2018, occurring within 4 weeks of last dose administration), then the EoT assessments will be conducted. Every reasonable effort should be made to have subjects return to the clinic for the final assessment.

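### After Week 96, Table 2.2 omits the pre-dose pregnancy test at 4-weekly doses that a healthcare provider still gives or supervises, although Section 7.5.3.11 requires one

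*Protocol*

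**What the plan says.** **Section 7.5.3.11.** Women of child-bearing potential "will have urine pregnancy tests pre-dose at all dosing visits and at EoT, as indicated in" Tables 2.1 and 2.2. The section then adds: "In the event of a positive urine pregnancy test at an HH visit, KRN23 will not be administered"; a serum sample is drawn to confirm. It describes experience in pregnancy as limited and the risks to mother and unborn child as unknown.

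**Table 2.2.** The first column (HH or telephone visit) is headed "Every 4 Weeks: 76, 80, 84, 88, 92, 100, 104, 112, 116, 124, 128, 136, 140, 148, 152" and continues as applicable to 30 September 2018. It marks drug administration and leaves the pregnancy-test row blank. The 12-weekly HH column and the 24-weekly clinic column mark both.

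**Footnotes 19 and 20.** Once competence is shown, subjects or caregivers inject at home: "they will be instructed to perform future study drug administrations at home without supervision for HH visits occurring after week 96 or later". Footnote 19 also says: "Drug administration by a HH nurse may continue at the discretion of the investigator, subject and/or caregiver". Footnote 20 sends a provider back every 12 weeks to assess pregnancy, among other things, but only for subjects who self-inject or whose caregiver injects.

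**Amendment 2, rationale for the Schedule of Events.** The result is put this way: "assessments previously made by the HH nurse, including pregnancy testing and vital signs, will no longer be collected during every HH visit". The ground offered for it is the new mode of injection: "Since supervision is no longer required in the event that drug is administered by the subject or caregiver".

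**The concern.** The rule that stops a dose after a positive test works only if a test precedes the dose. When a nurse gives a 4-weekly dose after Week 96, a site that follows Section 7.5.3.11 tests first and a site that follows Table 2.2 does not. Either site could be recorded as deviating from the protocol. A nurse who works from the table omits the check although she is present and able to do it. The consequence would be a dose given in an early pregnancy that a simple test might have caught. This is a matter of subject safety and clear site instructions. It does not affect any efficacy, pharmacodynamic or safety analysis.

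**Working it through.** No power or precision formula applies. The check is a count of the schedule, followed by a comparison of the texts.

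**1. Dosing calendar.** The Synopsis gives at most 184 weeks of treatment and 46 doses. Dosing every 4 weeks from Week 0 to Week 180 gives 180/4 + 1 = 46, so the stated figure is reproduced.

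**2. Drug row against pregnancy-test row.**

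| Part of schedule | Listed doses | With test | Without test |
|---|---|---|---|
| Table 2.1, Weeks 0 to 72 | 19 | 19 | 0 |
| Table 2.2, 4-weekly HH or telephone column | 15 | 0 | 15 |
| Table 2.2, 12-weekly HH column (108, 132) | 2 | 2 | 0 |
| Table 2.2, 24-weekly clinic column (96, 120, 144) | 3 | 3 | 0 |

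The Table 2.2 doses total 15 + 2 + 3 = 20, which is every fourth week from 76 to 152. The vital-signs row has the same blank in the 4-weekly column, and footnote 20 describes 12-weekly assessment. The blank is therefore a real entry and not a fault in reading the table.

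**3. Doses after Week 96.** There are 14 listed doses (Weeks 100 to 152). Tests fall at 108, 120, 132 and 144, so 14 − 4 = 10 have none: Weeks 100, 104, 112, 116, 124, 128, 136, 140, 148 and 152. Scheduled tests are 12 weeks apart, with at most two untested doses in a row.

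**4. Which of those 10 are in conflict?**

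- *Unsupervised injection.* The Synopsis says of these cases: "in such cases, the HH visit would become a telephone visit". The Amendment 2 rationale covers them directly, and footnote 20 supplies the 12-weekly test. The interval is a documented choice. What remains is that the wording of Section 7.5.3.11 was not updated.
- *Dose given or supervised by a provider.* Three routes lead here. Nurse dosing may continue under footnote 19. The same footnote returns dosing to supervision when more training is needed. Section 7.4.3 lets the investigator reinstate nursing visits. Section 7.5.3.11 asks for a test, the table shows none, no footnote restores it, and the reason for the reduction (no supervision needed) does not describe the situation.

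**5. Was the section reviewed?** Amendment 2 lists changes to the contraception and pregnancy-risk text of Section 7.5.3.11. The testing sentence and the HH withholding rule still stand in the current text, so the conflict is between two operative parts of one protocol.

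**The case against.** **The reduction was deliberate.** The Amendment 2 summary moves 4-weekly HH-nurse assessments to every 12 weeks in a sentence with no self-administration condition. The sponsor may have meant it to cover nurse-given doses too. This stands as far as intent goes. It does not settle the matter, because the reason given concerns only subject or caregiver injection and footnote 20 is limited to those subjects. If the wider reduction was meant, Section 7.5.3.11 is wrong as written.

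**The section defers to the tables.** It does end by pointing to them. On that reading, though, its statement about all dosing visits is untrue after Week 72 and still needs correcting.

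**A telephone-confirmed self-injection is not a dosing visit.** This is a fair reading, and it is why unsupervised doses are left out of the gap. It does not help for a dose given by a nurse.

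**The HH label does not show that a nurse attends.** Correct: the Amendment 2 summary says HH visits may take place without one. The gap must therefore be defined by who gives or supervises the dose.

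**Other safeguards exist.** Contraception is required, subjects planning pregnancy are excluded, and testing continues every 12 weeks. These lower the risk and keep the point small.

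**Conclusion.** The inconsistency is real and narrow. It concerns 4-weekly doses after Week 96 that a healthcare provider gives or supervises to a woman of child-bearing potential. The 10 listed weeks (and later ones, as applicable) show where such doses can fall. The documents do not say how many are provider-given or how many of the approximately 20 subjects are women of child-bearing potential, so the number of affected doses cannot be stated.

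Two stronger readings are tempting and are not supported:

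- *A reader might take 15 untested doses of 20 as the size of the defect.* That count includes unsupervised doses, for which 12-weekly testing is a documented choice. It also includes Weeks 76 to 92.
- *A reader might infer that the five untested doses at Weeks 76 to 92, before unsupervised dosing begins, are a live hazard.* Assume end of treatment on 30 September 2018 after 156 to 184 weeks (Section 7.4.5). The page date of 29 September 2017 is then 366/7 = 52.3 weeks earlier, which puts subjects at Weeks 103.7 to 131.7. The summary's date of 23 June 2017 is 464/7 = 66.3 weeks earlier, which puts them at Weeks 89.7 to 117.7. On the later date all five doses were past. On the earlier date only Week 92 could still lie ahead, for the latest entrants, and Section 8.1.1 requires IRB approval before a change takes effect. Changing those cells would protect almost no one.

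The point merits a correction because the safeguard is already in the protocol and is cheap to keep working.

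**What to change.** Two edits, which belong together:

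1. Add a footnote to the 4-weekly column of Table 2.2: *For women of child-bearing potential, when a healthcare provider gives or supervises the dose at an HH or clinic visit, a urine pregnancy test is done before dosing.*
2. Reword the timing in Section 7.5.3.11: *pre-dose at every dose given or supervised by a healthcare provider; for unsupervised doses after Week 96, at the 12- and 24-weekly visits in Table 2.2; and at EoT.*

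This leaves the sponsor's 12-weekly interval for unsupervised doses unchanged and gives sites one instruction. The cost is one footnote and one sentence in an amendment that needs IRB approval, plus one urine test at a visit already being made. An occasional false positive will need a serum test and will delay a dose.
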